2.3 Groups

All participants will be given a unique number by the time they are allocated in four groups (table 2), with the addition of the code number of each centre in front: (1 for Patras, 2 for Cyprus and 3 for Nancy). For each centre, participants with numbers 001 to 080 will belong to the Start Up Group (A), the 40 following will belong to the Main Group (B), the 25 following afterwards will belong to the Evaluation Group (C) and the last 25 to the Control Group (D). The Evaluation Group (C) will be further divided in two parts: participants with numbers 121-140 will belong to the "standard" Evaluation Group; while those with numbers 141-145 will belong to the Long Term Evaluation Group, with an augmented intensity of following up.

Group	Serial Number
A- Start Up	001-080
B- Main	081-120
C- Evaluation	121-145
Ci- Standard Evaluation	121-140
Cii- Long term Evaluation	141-145
D- Control	146-170
With the prefix of the centre number	1 for Patras, Greece
	2 for Nicosia, Cyprus
	3 for Nancy, France

Table 2. Participants' ID numbers

In case of exclusion or premature withdrawal of a participant, (s)he has been replaced by a new subject, to whom a new unique ID number has been given. The substitute subjects were given the number of the individual they have replaced with the addition of 500. For example, if the participant number 1094 withdrew from the study (subject number 94 from the first recruitment centre), the subject that replaced him/her will take the number 1594

(=1094+500). For subject number 3164 who withdrew (participant number 164 from the third recruitment centre), the subject replacing him/her will take the number 3664 (=3164+500). However, participants' replacements took place only until M19. Any subject that dropped off after July 2017, has not been and will not be replaced due to lack of time for catching up with the minimum follow up time period required (M19 represents the middle timeline of the project).

The number of the participants allocated in each group is already agreed in the original proposal and corresponds mostly to issues of availability of material and workforce in the context of actual financial potential and less to pure mathematical calculations, due to the originality of the project and the absence of a previous reference to consider for sample size calculations.

2.4 Sampling, recruitment procedure and randomization

The method of sampling from the general population will be the convenient method, in order to create a pool of candidate participants. Although it might not be the most unbiased method of recruitment, it is the most suitable for the present study mainly because our participants are actually volunteers. We addressed to them, in their natural environment (community settings, their own home) in order to ask them to voluntarily participate in the FrailSafe project.

The recruitment strategy will be organized by each one of the 3 centres individually. Main procedures that were followed are collaborations with older people's associations and public events in order to inform people about the importance of intervening on frailty and the objectives of FrailSafe study. More specifically, we approached medical institutions and rehabilitation centers, public organizations and local societies/associations, home care services, older people's and relatives' focus groups and individuals occupied with health care provision. In parallel, a communication policy by advertising in the mass media was attempted (local television channels, newspapers and websites), with very satisfying results.

The aforementioned strategy aims not only at attracting interested individuals eligible for the study, but also at spreading the word in people who are not necessarily eligible, but who could mobilize their friends and relatives and inform their personal or professional environment.

Inevitably, a certain degree of motivation bias is inherited in this project, and cannot be fully excluded. Potential participants in all centers were asked to participate after explaining the study procedures in details. Individuals who were not motivated declined to consent. To overcome, as much as possible, this issue was stressed the future benefits of the study, as well as the activities and interaction during the study that may spice up the daily routine.

Despite the overall common procedures, different enrollment strategies were somehow proved to be more effective in each clinical center. For instance, INSERM (France) mainly carried out public targeted meetings inviting older people to participate, whereas in Patras (Greece) the local Geriatric and Gerontology Society mainly invited its members to participate, and similarly MATERIA (Cyprus). Therefore in the whole, the study sample was not made only by self-volunteered participants.

By this extrovert approach a pool of interested individuals is created and eligible participants (subjects who seemingly fulfil the inclusion and non-inclusion criteria) are been called by telephone to make a first appointment.

During this first meeting the individual are thoroughly informed (information letter and supplementary oral information), questions are answered and, in case of agreement, an informed consent is signed. Data regarding social interaction and natural language analysis is collected. A first clinical evaluation follows (part of the clinical evaluation battery-section 3.1) in order to investigate the Fried's criteria of frailty, comorbidities and cognitive status (tables 6, 9 and 13). This information is necessary for:

- The classification into frailty categories. The participants will be classified in three groups according to their frailty status assessed by the criteria of Fried's frailty index (1) (table 9). Individuals with 3 or more criteria will be allocated in the frailty category, those with 1-2 criteria will be characterized as pre-frail, while those with no frailty criterion will be characterized non frail.
- Identification of leader co-morbidities: history of stroke, mild cognitive impairment (MCI), osteoarthritis for men and osteoporosis for women.
- The verification of inclusion and non-inclusion criteria. In case of exclusion, replacement of the participant with another subject will take place. For this reason the pool of our candidate participants should be considerably larger than the number of subjects that actually need to be recruited.

The proportion of subgroups ("non-frails", "pre-frails", and "frails") according to the Fried's frailty criteria was changed from the initial 2:1:1, i.e. non-frail (50%): pre-frail (25%): and frail (25%), to 1.5 : 1.5 : 1 for groups A and B added up together.

This proportion is more favorable and exploitable due to the following reasons:

- We considered the risk that there will not be enough users to achieve project's objectives related to frailty itself as pointed out by the experts in the 1st review of Frailsafe (see recommendations FR1 and FR2). The project focuses mostly on non-frail and pre-frail people since the frail group does not offer much in monitoring the transition between states.
- Non-frail and mostly pre-frail individuals are more likely to benefit from interventions in terms of prevention of evolution of their frailty status (MO3), than the already frail ones that are less likely to regress to a previous frailty status.
- Especially the pre-frail individuals, that outweigh other categories in our population, are those who are traditionally considered to benefit more from potential interventions and thus are generally the target of the standard CGA (ie, excluding patients who are either too well or are too sick to derive benefit) (MO4) (1). If the

FrailSafe system is to be tested for its added value on the standard CGA (main medical objective), pre-frail individuals should be the dominant target group.

- Our study focuses on prevention (MO6), therefore, a smaller number of already frail people should be allowed. However, they should also exist in our study population in order to enable us to make comparisons and draw conclusions.
- From the very first analysis that has been performed and presented in D2.6 Behavioral management, we observe that the pre-frail category almost constantly scores in between the performances of the non-frail and the frail group in all tests and parameters. This emphasizes the fact that they constitute a dynamic intermediate category with the potential to approach either the one or the other extreme (MO5). Thus, the results of potential interventions could be measurable and could contribute to the prevention of category shifting towards frailty.
- Under the prism of a potential exploitation of the FrailSafe end product in the future, individuals, health care professionals, insurance companies and health policy makers could be more interested to apply the integrated FrailSafe system in people that are already threatened by a devastating health condition such as frailty (ie the pre-frails), rather than devoting resources in a totally healthy population, who might not be eligible for reimbursable health interventions. Therefore this frailty category is considered to be of great interest for the FrailSafe project (MO7).

The above listed proportions are calculated on the total of participants, in the sum from all three centers, so different percentages may be present within groups from Cyprus, Greece and France. However, the same criteria (Fried's)(2) (table 9) will be applied in all clinical centers.

This stratification of frailty according to Fried's criteria will not be used in the analysis of data. The study population will be considered as a whole, from which new frailty metrics will be identified using both hard and proxy outcomes; the latter will be based on the change of clinical and FrailSafe parameters.

The sample in this study should ideally be randomly selected from the general population in those aged \geq 70 years. This would require a larger number of participants and a larger number of study workforce, as well as equipment, in order to include individuals with the right case mix of frailty levels and a representative number of comorbidities. Undoubtedly, such a design would have been preferred and would have provided strong and reliable clinical results. However, current financial resources in this Horizon 2020 call, which are split among technological development and clinical evaluation, were not sufficient for this type of methodology.

It is understandable that transition among the groups as defined by Fried's criteria might not be easily observed with the current study design, as number of participants, time span and number of simultaneous FrailSafe assessments are limited. On the other hand, functional changes or proxy outcomes expressing loss of functional reserve is likely to be detected when the study group is examined as a whole. The choice of the current clinical study methodology was a compromise between an ideal approach and a more practical solution, though hampered by numerous limitations.

In addition, in each of the three frailty status, at least 7 have prior stroke, 7 MCI (Mild Cognitive Impairment), 7 either osteoporosis for women or osteoarthritis for men and 7 nothing of the mentioned above. There is no particular concern in which group they will

belong. If this will not be achieved by randomization, the investigator, who will be in charge to overall monitor randomization, will intervene to further randomly stratify cases to obtain this pre-specified study objective.

The sample was recruited after specifying lower age limits and certain comorbidities. The intention which was described and accepted in the initial proposal, was to include certain key comorbidities, which are in a relatively low prevalence in elderly population. Otherwise, these comorbidities would have been under representative in our small sample, and their effect on frailty process might have been lost. These comorbidities, among many others equally important, may accelerate the frailty process; they may also influence the scoring of frailty according to Fried's criteria. For instance a previous stroke or the presence of osteoarthritis may slow down the speed of walking altering the frailty score, whilst at the same time would not contribute to a functional worsening in time. Mild cognitive impairment may have an opposite effect, as it does not directly modify the Fried frailty score, but may strongly influence the loss of functional reserve.

During clinical evaluation, together with the pre-specified comorbidities, up to twenty seven other possible medical conditions/comorbidities are also recorded. Thus, the analysis of data regarding comorbidities will not be carried out exclusively around the pre-specified ones. The absolute number of accumulated comorbidities, the absolute number of the most prevalent comorbidities, and a choice of the most prevalent comorbidities will be explored as independent or confounding factors to the frailty process. An effect on functional change may be shown by adding or subtracting groups of individuals with common comorbidity/ies.

Randomization will take place for groups C (Evaluation) and D (Control)(section 2.4) in a later study period (M10-M30). The randomization has proven to be practically difficult for groups A (Start Up) and B (Main), due to the almost coincidence of their recruitment in the beginning of the study and the large number of participants they required. As the dissemination campaign advanced progressively, it turned out to be difficult to have in our availability, since the very initial phase of the clinical study, an even larger pool of participants in order to strictly randomise them. Instead, we included in the first group the first 80 subjects that expressed their interest for participation in each centre, followed by the 40 consequent ones, who were finally allocated to group B. We estimate that since in the present phase of the clinical study the objective is to validate the FrailSafe system and to test its detection sensitivity and not to compare interventions (as will be during the groups C and D parallel evaluations), and since we have no reason to believe that the subjects who were recruited during the first dissemination activities differ significantly from those who were informed about the study in a later stage of the recruitment campaign, the consortium believes that this lack of randomization in the very first phase of the study will not affect results, since comparison between groups will take place later between group C (evaluation) and D (control).

In a later period during the study (M20-M30), recruitment campaigns will start again in order to create the pool of eligible subjects from which participants for group C and D will be randomly selected.

In addition, the participants of the evaluation group C will be further randomized (1:1) into two categories either to receive a tailored set of lifestyle, nutrition and exercise recommendations (predetermined recommendation and "intervention" proposals based on the monitoring performed using the Frailsafe system) or to receive general life style recommendations (standard care). The technical personnel responsible for the extraction and analysis of data will be blind on randomization procedure.

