2.1 Study's objectives and overall design

FrailSafe clinical study's main objectives are:

To better understand frailty and its relation to co-morbidities

- To identify quantitative and qualitative measures of frailty (through advanced data mining approaches on multiparametric data) and use them to predict short and longterm outcome and risk of frailty
- To develop real life sensing and intervention platform offering physiological reserve and external challenges
- To provide a digital patient model of frailty sensitive to several dynamic parameters, including physiological, behavioural and contextual
- To create "prevent-frailty" evidence-based recommendations for the elderly; to strengthen the motor, cognitive, and other "anti-frailty" activities through the delivery of personalised treatment programmes, monitoring alerts, guidance and education
- To achieve all with a safe, unobtrusive and acceptable system for the ageing population while reducing the cost of health care systems.

The main objective of the FrailSafe study could be summarized in the investigation of the added value that brings the integrated FrailSafe system on the standard clinical approaches of frailty, in terms of earlier and more accurate detection and even prediction of its evolution.

FrailSafe study is an interventional, non-pharmacological, cohort study testing the efficacy of a series of novel instruments aiming to detect and quantify frailty. During its development (36 months), 510 older individuals living in the community will be enrolled and followed up in terms of their health conditions. During the primary phases of the study (M4-M30), intensive clinical studies will be performed aiming to provide sufficient data for the quantification of the FrailSafe computational models and augmented reality framework (ground the models and algorithms with experimental data, quantify and fine tune the intervention services). During the test and evaluation period (M31-M36) the clinical studies will focus on evaluating and validating FrailSafe developments.

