5.1 Definition of Frailty Indices

In order to render clinical results measurable, there is a need to define loss of reserve, independently of frailty status as this is defined by Fried's criteria.

On the other hand, FrailSafe Database contains variables at different time points from

- Clinical Evaluation
- Follow up assessment

• FrailSafe system metrics

In this scope, a new combined index (**Combined Frailty index: CoFI**), that will express frailty status relevant to the study's measurements, will be created by adding up two other frailty indices derived from the study, the **Clinical Frailty Index (CIFI**), corresponding to the results of the clinical evaluation, and the **Technical Frailty Index (TFI**), corresponding to the metrics derived from the FrailSafe system devices.

Table 21. Frailty Indices definition

CIFI (Clinical Frailty Index): score corresponding to the findings of the clinical evaluation in a time-spot (Appendix I)
TFI (Technical Frailty Index): accumulated score derived from the FrailSafe system
metrics during certain time intervals of observation (Appendix II)
Co FI (Combined Frailty index): combined Clinical and Technical frailty score

Each time a programmed clinical evaluation is effectuated, a CIFI score will be calculated, which will be composed by several items that correspond to various aspects of frailty, as they are described by the clinical evaluation sub-questionnaires

[figure not shown]

Figure 6. Example of Frailty Indices for a subject belonging to group A.

Similarly, a TFI will be calculated for each FrailSafe system installation, practically, for each FrailSafe home visit. For example, for group A, there will be 2 TFIs calculated, TFIA1 and TFIA2. Similarly for group B there will be 7 TFIs calculated.

Finally, for example for group A, a combined FI, by adding up CIFI and TFI will be calculated twice: CoFIA1=CIFIA1+TFIA1 and CoFIA2=CIFIA2+TFIA2.

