5.3 Hypothesis Generation

According to outcomes and Frailty Indices definitions, the medical objectives of the study can be operationally approached as described in table 24.

Table 24. Hypothesis Generation for the analysis of data per MO

M01.	(Understanding frailty and relation to co-morbidities)
	What is the relation of most prevalent comorbidities with Clinical Frailty Index and with proxy and hard outcomes.
MO2	(Develop quantitative and qualitative measures to define frailty)
	Assess the ability of the Technical Frailty Index to describe reduced reserves, as expressed by Clinical Frailty Index and proxy and hard outcomes
MO3	(Use these measures to predict short and long-term outcome)
	Evaluate the ability of each component of the Clinical or Technical Frailty Indices, and/or combination of those, to predict Proxy and Hard Outcomes
MO4	(Develop real life tools for the assessment of physiological reserve and external challenges)
	Identify the influence of each component of the Combined Frailty Index to best predict proxy and hard outcomes, in order to validate the predictive value of the Combined Frailty Index.
M05	(Provide a model sensitive to change)
	Identify the sensitivity of each component of the Combined Frailty Index to describe shift in reserve as a holistic measure defined by the proxy and hard outcomes
MO6	(Create "prevent-frailty" evidence based recommendations)
	Assess if positive attitude or changes, that took place in each and every aspect of the frailty sub-indices, contribute to a modification of the expected patterns

	of the proxy and hard outcomes, so as to be proposed as clinical recommendations
	For example, a recommendation could be provided for physical, cognitive or social actions, which have been tested during the study and have shown a positive profile in regards of proxy and hard outcomes.
M07	(Achieve all with a safe and acceptable to older people system)
	Constantly evaluate and record the acceptability and safety aspect of the FrailSafe system application and the totality of the procedures followed during the study.

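### The main objective is added value over standard clinical frailty assessment, but no hypothesis in Table 24 tests what the device index adds to the clinical index.

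*Protocol*

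**What the plan says.** **Objective.** Section 2.1 describes the main objective as "investigation of the added value that brings the integrated FrailSafe system on the standard clinical approaches of frailty", by which it means detecting frailty sooner and more precisely and predicting its course. Section 2.4 makes the standard specific: the "FrailSafe system is to be tested for its added value on the standard CGA (main medical objective").

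**Indices.** Section 5.1 builds CoFI by simple addition, for example "CoFIA1=CIFIA1+TFIA1". CIFI (Appendix I, Table 22) is an equally weighted sum of clinical evaluation items. TFI (Appendix II) is tuned on groups A and B.

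**Hypotheses (section 5.3, Table 24).** MO2 relates TFI to CIFI and to proxy and hard outcomes. MO3 takes components of either index, and combinations, as predictors. MO4 examines the influence of each CoFI component "in order to validate the predictive value of the Combined Frailty Index". MO5 concerns the sensitivity of CoFI components to change. MO1, MO6 and MO7 cover comorbidities, recommendations, and safety with acceptability.

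**Device variables.** Section 5.2.2 identifies the important ones as those that correlate well, possibly with a lag, with the fitted proxy variables.

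**Fried categories.** Section 2.4 says that the stratification by Fried's "criteria will not be used in the analysis of data". Section 5.1 defines loss of reserve "independently of frailty status as this is defined by Fried's criteria". Section 3.6.1 nevertheless selects 20 participants from each Fried category to study the effect of frailty on cardiovagal control.

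**The concern.** Added value is a contrast between standard assessment plus devices and standard assessment alone. A study can find that TFI tracks CIFI, that some components predict, and that CoFI predicts, and still not know whether the devices contribute anything beyond the clinical visit. Because CoFI contains CIFI, its predictive performance does not separate the two sources. Followed as written, the study could report a validated combined index with no direct evidence on its main question.

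**Working it through.** **1. Objective against hypotheses.** Each row of Table 24 is checked for a contrast of the form TFI given CIFI, or CoFI against CIFI, on the same outcome in the same participants.

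| Row | What it asks | Isolates added value? |
|---|---|---|
| MO1 | Comorbidities against CIFI and outcomes | No |
| MO2 | TFI against CIFI, and TFI against outcomes | No. Agreement with CIFI may mean redundancy; the association with outcomes is not conditional on CIFI |
| MO3 | Components or combinations predicting outcomes | No. No reference model is named |
| MO4 | Influence of CoFI components; CoFI predicts outcomes | No. CoFI includes CIFI |
| MO5 | CoFI components' sensitivity to change | No |
| MO6, MO7 | Recommendations; safety and acceptability | No |

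**2. Selection of device variables.** The rule in section 5.2.2 rewards a device variable for resembling a proxy (gait speed, MoCA or MMSE, GDS, weight loss, self-rated health). All of these are also CIFI items in Table 22. A variable that merely duplicates the clinical measurement scores well.

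**3. What the Fried sentence excludes.** Table 22 contains items matching all five Fried criteria: weight loss, exhaustion, grip strength, gait speed and low physical activity. The sentence therefore removes the three-level category, not the underlying measurements and not the CGA.

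**4. Illustration of why CoFI alone cannot answer the question.** The protocol gives no figure to reproduce: no alpha, power or effect size. Inputs:
- N = 3 centres × (80 + 40) = 360, groups A and B (section 2.3).
- Assumed: TFI is pure noise; ρ is the correlation of CIFI with the outcome; r = var(TFI)/var(CIFI); two-sided 5% level.

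Formulae: corr(CoFI, outcome) = ρ/√(1 + r); power ≈ Φ(atanh(corr) × √(N − 3) − 1.96).

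For ρ = 0.3 and r = 1: corr = 0.3/√2 = 0.212. Then atanh(0.212) × √357 ≈ 4.07, and Φ(4.07 − 1.96) ≈ 0.98.

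| ρ | r = 0.5 | r = 1 | r = 2 |
|---|---|---|---|
| 0.2 | corr 0.163, power 88% | 0.141, 77% | 0.115, 59% |
| 0.3 | 0.245, >99% | 0.212, 98% | 0.173, 91% |
| 0.4 | 0.327, >99% | 0.283, >99% | 0.231, 99% |

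A logistic simulation gives the same picture. It used n = 360, about 30% events, equal variances, noise TFI, and log-odds of 0.4, 0.55 and 0.7 per SD of CIFI. CoFI was significant in about 64%, 88% and 99% of data sets (repeat runs agree within about three points). Mean AUC fell from 0.61, 0.65 and 0.68 for CIFI alone to 0.58, 0.60 and 0.63 for CoFI. The likelihood-ratio test of TFI added to CIFI rejected in about 4% to 5%, its nominal rate.

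**The case against.** The strongest reply is that the plan contains more than CoFI, and it carries weight.

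- **A reader might infer that the standard comparator is barred.** It is not. Section 2.4 names the CGA as the standard, and the CGA is analysed as CIFI. Only the Fried stratification is dropped, for stated reasons: transitions between categories may not be easily observed, and stroke or osteoarthritis can alter the score without functional worsening.
- **A reader might infer that only the combined index is validated.** That is also wrong. Appendix I plans to validate CIFI against outcomes, and MO2 and MO3 examine TFI and the components of both indices.
- **A reader might infer that a useless device score would pass.** The documents state no rule under which one significant CoFI term means success. A pure-noise TFI would fail a 5% test under MO2 about 95% of the time. Sections 5.4.2 and 5.4.2.1 also foresee stepwise elimination and AIC or BIC. Applied to TFI added to CIFI at n = 360, BIC would keep a noise TFI in about 1.5% of studies (chi-square above ln 360 = 5.89) and AIC in about 16% (chi-square above 2).

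What does not stand is the step from intent to test. Section 2.1 speaks of comparing tools, section 5.2.2 of device variables possibly giving additional knowledge, and section 5.4.2.2 of added value through the eFI. None defines the contrast, and the generic selection tools are not tied to TFI given CIFI. MO2 stops noise, but not redundancy: a TFI that merely duplicates CIFI would pass MO2 and MO4 alike.

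Model and metric can be left to a statistical analysis plan. The contrast itself belongs in Table 24, because that table is where the protocol turns its objectives into hypotheses.

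**Conclusion.** The concern holds in this form: the stated main objective has no matching hypothesis, and neither MO4 nor the selection rule in section 5.2.2 can separate added value from the clinical signal or from redundancy. This follows from the text alone. The numerical results are illustrative and rest on an assumed pure-noise TFI, assumed variance ratios, an assumed 30% event rate in the simulation and a single-term significance rule that the protocol does not state. Section 5.4.2.3 itself expects few hard outcomes. They show only that CoFI predicting outcomes is weak evidence for the devices, not that the study will reach a false claim at those rates.

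Separately, the sentence in section 2.4 on Fried status and the Fried grouping in section 3.6.1 should be reconciled.

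**What to change.** 1. Add to MO2–MO4 in Table 24 one comparison in the same participants: a base model with CIFI, age, sex and centre, against that model plus TFI. Apply it to the hard outcomes and to change in the proxy outcomes.
2. Report the likelihood-ratio test and the change in discrimination, with cross-validation split by participant. Repeat the tuning of TFI and the selection of device variables inside each training set, because both draw on groups A and B.
3. State that added value will be claimed only from this comparison, not from CoFI predicting outcomes.
4. Limit the section 2.4 sentence so that Fried status may serve as a separate sensitivity benchmark, and make it consistent with section 3.6.1. Do not put Fried status in the same base model as CIFI, which already contains its items.

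Cost: a little more analysis on data the study already plans to collect, with no extra visits or measurements. The added-value claim becomes harder to reach.
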